6.1.1.1 Screening Failure

Subjects whose screening test results fail to satisfy the inclusion/exclusion criteria of this clinical study may not participate in the clinical study. The reasons for screening failure of these subjects who are ineligible to participate in the clinical study shall be recorded in the screening log. If screening fails, screening continues until the target number is met.

6.1.2 Visit 2 (Administration 1, Day 0)

6.1.2.1 Before Administration of Investigational Product

The following shall be performed prior to administering the investigational product.

Hospitalization (if applicable)

Subjects shall be hospitalized on the day before administration of the investigational product and their vital signs shall be measured. If they are not hospitalized, vital signs may be omitted, and the hospitalization day in the case report form shall be recorded the same as the test day prior to administration.

· Final confirmation of inclusion/exclusion criteria

Assignment of allocation numbers* when inclusion/exclusion criteria are satisfied
 *: See section 5.3.4 Assignment of Subject Numbers

Body measurement (weight measurement)

A subject's weight shall be measured at Visit 1 and throughout the clinical study every time a subject makes a visit (shall be performed prior to administering the investigational product at Visits 2, 3, 4, and 5).

Complete blood cell count

This shall be performed at Visit 1 and throughout the clinical study every time a subject makes a visit (shall be performed prior to administering the investigational product at Visits 2, 3, 4, and 5). However, if there is a subject with abnormal findings in the test at Visit 3 (Day 14), a complete blood cell count and a general blood chemistry test may be performed at Day 30 depending on the decision of the principal investigator. The complete blood cell count items are as follows:

WBC, RBC, Hb, Hct, MCV, MCH, MCHC, PLT, ESR, MPV, differential count of WBC (Band neutrophil, Segmented neutrophil, Basophil, Lymphocyte, Monocyte)

General blood chemistry test

This shall be performed at Visit 1 and throughout the clinical study every time a subject makes a visit (shall be performed prior to administering the investigational product at Visits 2, 3, 4, and 5). However, if there is a subject with abnormal findings in the test at Visit 3 (Day 14), a complete blood cell count and a general blood chemistry test may be performed at Day 30 depending on the decision of the principal investigator. Since a blood glucose test is included, the subject shall maintain an 8-hour fasting state prior to the test. The general blood chemistry test items are as follows:

total protein, albumin, globulin, A/G ratio, cholesterol, total bilirubin, AST, ALT, fasting glucose, BUN, creatinine, estimated GFR, Ca²⁺, phosphate, Na⁺, K⁺, Cl⁻, CRP, triglyceride, HDL-cholesterol, LDL-cholesterol

· Sample collection for retrospective biomarker study

The serum of subjects shall be collected and stored frozen at -70°C. All blood samples are stored with unique numbers for retrospective biomarker study after all personal information is deleted.

Urinalysis with microscopy

This shall be performed at Visit 1 and throughout the clinical study every time a subject makes a visit (shall be performed prior to administering the investigational product at Visits 2, 3, 4, and 5). However, if there is a subject with abnormal findings in the test at Visit 3 (Day 14), urinalysis with microscopy may be performed at Day 30 depending on the decision of the principal investigator.

The urinalysis items are as follows:

Color, turbidity, specific gravity, pH, albumin, glucose, ketones, bilirubin, blood, urobilinogen, nitrite, leukocyte esterase, microscopy (RBC, WBC, casts)

Vital signs

Vital signs including blood pressure (measurement shall be taken with the subject in a sitting position after resting for at least 10 minutes prior to measurement), temperature, heart rate per minute, and respiratory rate per minute shall be measured. The measurement results shall be recorded in the subjects' case report forms. This shall be performed at Visit 1 (screening) and throughout the clinical study every time a subject makes a visit (on the drug administration days consisting of Visits 2, 3, 4, and 5, it shall be performed both prior to administration and 2 ± 1 hours after administration). However, if there is a subject with abnormal findings in the test at Visit 3 (Day 14), a follow-up test may be performed at Day 30 depending on the decision of the principal investigator.

Concomitant medications survey

The brand names and ingredient names of concomitant medications shall be surveyed at every visit and recorded in the case report form. All medications and treatments administered within 6 months before Visit 1 (screening) shall be surveyed. Previous medications and previous treatments shall be defined as all previously collected medications and treatments before Visit 2 (first administration of investigational product). Concomitant medications and treatments shall refer to all medications that have been administered at least once starting from Visit 2 (first administration of investigational product) and throughout the clinical study. The categories of collected medications and treatments shall follow this definition. The following shall also be surveyed for each medication:

Brand name

- · Indications for medication administration (reason for administration)
- · Dose/strength, administration route, number of administrations
- Start and discontinuation dates of administration (whether to continue when the clinical study is terminated)

Neurologic exam

This shall be performed for CMTNS-v2 measurement, and the investigator shall perform the neurologic exam (motor system: muscle strength; sensory system: nociception, pallesthesia) on a subject as follows:

Table 10. Neurologic exam items and procedures for CMTNS-v2 measurement

Test Item	Procedure
Muscle strength	Reduced muscle strength is referred to as weakness or paresis, and the loss of strength is referred to as paralysis. To measure the muscle strength of limbs, the flexion (C5-6) and extension of wrist joint, extension of wrist (C6-8), grasping test (C7-T1), abduction of finger (C8-T1, ulnar nerve), and opposition of thumb (C8-T1, median nerve) shall be tested in the upper limbs. For the strength of intrinsic hand muscles, only the two muscles of the abductor pollicis brevis (APB) and the first dorsal interosseous (FDI) shall be evaluated, and the stronger of the two shall be scored. In the lower limbs, the flexion (L2-L4), adduction (L2-L4), and extension (S1) of hip joint, the extension (L2-L4) and flexion (L4-S2) of knee, as well as the dorsiflexion (L4-5) and plantar flexion (S1) of ankle shall be tested.
	The results of performing a muscle strength test of the limbs in a subject shall be indicated using the Medical Research Council (MRC) grade*. * MRC grade (Motor power) 0: Complete paralysis I: Flicker of contraction possible II: Movement possible if gravity eliminated III: Movement against gravity but not resistance IV: Movement possible against some resistance V: Power normal (it is not normally possible to overcome a normal adult's power)
Nociception	Stimulation shall be applied by alternately using tools with a dull end and a sharp end, and it shall be verified whether these can be distinguished. When comparing the left and right sides of the body, stimulation shall be applied to the same sites. Then, the subject shall be asked whether the sensations are the same.
Pallesthesia	Vibration shall be applied to a low-pitched tuning fork (a Rydel-Seiffer tuning fork shall be used), and this shall be placed on the distal joints of the hands and feet to verify that the subject feels the vibrating sensation. Pallesthesia is the first sensation lost in peripheral nerve disorders.

CMTNS-v2

Charcot-Marie-Tooth Neuropathy Score-version 2 (CMTNS-v2) is a measurement tool for

evaluating the severity of disease.[66] Measurements shall be taken for 9 items which include 3 items for disease symptoms, 4 items for signs, and 2 items for neurophysiological testing. The severity of disease shall be classified according to scores as mild (≤10), moderate (11 to 20), and severe (>20). This clinical study shall target mild to moderate patients. This shall be performed at Visit 1 (screening), Visit 2 (Day 0), and Visit 7 (termination visit, Day 270) (shall be performed prior to administration at Visit 2 [Day 0]). See "Appendix 4. CMTNS-v2" for details.

Anti-HGF Ab test

The antibody test for hepatocyte growth factor shall be performed at Visit 2 (Day 0) and Visit 7 (termination visit, Day 270) (shall be performed prior to administration at Visit 2 [Day 0]). The serum of subjects shall be collected and stored frozen at -70°C. When the collection of blood from all subjects is completed, the samples shall be sent to the central laboratory all at once for analysis.

MRI leg

The muscles of lower limbs shall be imaged, and the fatty infiltration level of the leg muscles injected with the investigational product shall be measured and evaluated as fat content value (%) at one level for each muscle.[67]

The test days shall be at Visit 2 (Day 0) and Visit 7 (termination visit, Day 270) (shall be performed prior to administration at Visit 2 [Day 0]).

FDS

The functional disability scale (FDS) assesses a patient from 0 to 8 points as shown below depending on the patient's mobility.[68] The assessment days shall be at Visit 2 (Day 0), Visit 4 (Day 90), Visit 6 (Day 180), and Visit 7 (termination visit, Day 270) (assessment shall be performed prior to administration at Visit 2 [Day 0] and Visit 4 [Day 90]).

0=normal;

1=cramps and fatigability;

2=inability to run;

3=possible unaided;

4=with cane;

5=with crutch;

6=with walker;

7=wheelchair;

8=bedridden.

ONLS leg scale

The overall neuropathy limitation scale (ONLS) is a tool for measuring the activity level of patients with peripheral neuropathy. [69] It is scored by separately categorizing arms and legs. Measurement shall be performed only on legs in this clinical study. The measurement day shall

be at Visit 2 (Day 0), Visit 4 (Day 90), Visit 6 (Day 180), and Visit 7 (termination visit, Day 270) (measurement shall be performed prior to administration at Visit 2 [Day 0] and Visit 4 [Day 90]). See "Appendix 5. ONLS Leg scale" for details.

10MWT

This is a test that measures the time required for a subject to walk 10 meters.[70] A subject shall be made to walk at a desired speed while wearing shoes. The subject shall be allowed to use an assistive device that the subject normally uses, if any. The subject shall be made to walk a corridor that is 14 meters long, and the time taken to walk 10 meters shall be measured with a stopwatch provided by the sponsor (time taken to pass 10 meters excluding 2 meters each for the starting and ending portions). The assessment day shall be at Visit 2 (Day 0), Visit 4 (Day 90), Visit 6 (Day 180), and Visit 7 (termination visit, Day 270) (assessment shall be performed prior to administration at Visit 2 [Day 0] and Visit 4 [Day 90]).

The starting point at 2 meters, the point for ending measurement at 12 meters, and the point for end of walking at 14 meters shall be marked in advance along the corridor.

See "Appendix 6. 10MWT (10-meter walk test)" for details.

Electroneurography (CMAP, SNAP, NCV)

The test days shall be at Visit 2 (Day 0) and Visit 7 (termination visit, Day 270) (shall be performed prior to administration at Visit 2 [Day 0]).

See "Appendix 7. Nerve Conduction Study (NCS)" for details.

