3.9 Rationale for Establishing Dose of Investigational Product

The administration dose of VM202, the investigational product of this study, has been established based on the results of nonclinical studies, as well as the administration doses and pharmacodynamic assessments in past clinical studies.

Rationale 1. Nonclinical Study Results

(1) Single-dose toxicity study

A single intramuscular dose toxicity study and a single intravenous dose toxicity study were

conducted in rats. Even when a dose of 6.840 mg/kg was administered, toxicity reactions, including death due to the drug were not shown in either males or females.

(2) Repeat-dose toxicity study

A 4-week intermittent intramuscular repeat-dose toxicity study (1.2 mg/kg/day, once a week, 5 doses in total) in rabbits, as well as a 13-week intermittent intramuscular repeat-dose toxicity study (3.420 mg/kg/day, once a month, 4 doses in total) in rats were conducted. Except for minor and transient irritations on the injection site, target organs with toxicological findings were not identified.

Table 3. Toxicity study results

[figure not shown]

¹⁾ NOAEL: no-observed-adverse-effect level, 2) HED: human equivalence dose

Rationale 2. Previously Conducted Clinical Studies

Starting with the phase 1 clinical study on angina pectoris in South Korea in 2007, as of 2020, six clinical studies in total have been conducted in South Korea and the United States (see section 3.8). The administration dose in each clinical study is as follows:

Table 4. Administration dose per visit in past clinical studies

Rationale 3. Pharmacodynamic Assessment of Investigational Product (VM202)

The results of measuring the residual quantity of VM202 for the pharmacodynamic assessment of the investigational product (VM202) in the phase 1/2 clinical study on patients with amyotrophic lateral sclerosis showed that the drug was not detected at 3 months post-administration of VM202 (see section 3.8.5).

Results for Rationale of Dose Establishment

The results of nonclinical studies showed that the no-observed-adverse-effect levels (NOAEL) of Engensis (VM202) were estimated to be \geq 6.840 mg/kg in rats and \geq 1.2 mg/kg in rabbits. No abnormal findings were shown in terms of safety and tolerability when 64 mg of VM202 in total was administered 4 times at one-week intervals (Weeks 0, 1, 2, and 3) in a phase 1/2 clinical study in patients with amyotrophic lateral sclerosis.

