6.1.5 Visit 4 (Third Administration, Day 90 ± 7)

6.1.5.1 Before Administration of Investigational Product

The following shall be performed prior to administering the investigational product.

Adverse event assessment

Information on newly developed or worsened adverse events, or adverse events that disappeared since the last visit shall be collected.

Body measurement (weight measurement)

A subject's weight shall be measured at Visit 1 and throughout the clinical study every time a subject makes a visit (shall be performed prior to administering the investigational product at Visits 2, 3, 4, and 5).

Complete blood cell count

This shall be performed at Visit 1 and throughout the clinical study every time a subject makes a visit (shall be performed prior to administering the investigational product at Visits 2, 3, 4, and 5). However, if there is a subject with abnormal findings in the test at Visit 3

(Day 14), a complete blood cell count and a general blood chemistry test may be performed at Day 30 depending on the decision of the principal investigator.

The complete blood cell count items are as follows:

WBC, RBC, Hb, Hct, MCV, MCH, MCHC, PLT, ESR, MPV, differential count of WBC (Band neutrophil, Segmented neutrophil, Eosinophil, Basophil, Lymphocyte, Monocyte)

General blood chemistry test

This shall be performed at Visit 1 and throughout the clinical study every time a subject makes a visit (shall be performed prior to administering the investigational product at Visits 2, 3, 4, and 5). However, if there is a subject with abnormal findings in the test at Visit 3 (Day 14), a complete blood cell count and a general blood chemistry test may be performed at Day 30 depending on the decision of the principal investigator. Since a blood glucose test is included, the subject shall maintain an 8-hour fasting state prior to the test.

The general blood chemistry test items are as follows:

total protein, albumin, globulin, A/G ratio, cholesterol, total bilirubin, AST, ALT, fasting glucose, BUN, creatinine, estimated GFR, Ca²⁺, phosphate, Na⁺, K⁺, Cl⁻, CRP, triglyceride, HDL-cholesterol, LDL-cholesterol

Sample collection for retrospective biomarker study

The serum of subjects shall be collected and stored frozen at -70°C. All blood samples are stored with unique numbers for retrospective biomarker study after all personal information is deleted.

Urinalysis with microscopy

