6.1.6 Visit 5 (Fourth Administration, Day 104 ± 7)

6.1.6.1 Before Administration of Investigational Product

The following shall be performed prior to administering the investigational product.

Adverse event assessment

Information on newly developed or worsened adverse events, or adverse events that disappeared since the last visit shall be collected.

Body measurement (weight measurement)

A subject's weight shall be measured at Visit 1 and throughout the clinical study every time a subject makes a visit (shall be performed prior to administering the investigational product at Visits 2, 3, 4, and 5).

Complete blood cell count

This shall be performed at Visit 1 and throughout the clinical study every time a subject makes a visit (shall be performed prior to administering the investigational product at Visits 2, 3, 4, and 5). However, if there is a subject with abnormal findings in the test at Visit 3 (Day 14), a complete blood cell count and a general blood chemistry test may be performed at Day 30 depending on the decision of the principal investigator.

The complete blood cell count items are as follows:

WBC, RBC, Hb, Hct, MCV, MCH, MCHC, PLT, ESR, MPV, differential count of WBC (Band neutrophil, Segmented neutrophil, Eosinophil, Basophil, Lymphocyte, Monocyte)

General blood chemistry test

This shall be performed at Visit 1 and throughout the clinical study every time a subject makes a visit (shall be performed prior to administering the investigational product at Visits 2, 3, 4, and 5). However, if there is a subject with abnormal findings in the test at Visit 3 (Day 14), a complete blood cell count and a general blood chemistry test may be performed at Day 30 depending on the decision of the principal investigator. Since a blood glucose test is included, the subject shall maintain an 8-hour fasting state prior to the test.

The general blood chemistry test items are as follows:

total protein, albumin, globulin, A/G ratio, cholesterol, total bilirubin, AST, ALT, fasting glucose, BUN, creatinine, estimated GFR, Ca²⁺, phosphate, Na⁺, K⁺, Cl⁻, CRP, triglyceride, HDL-cholesterol, LDL-cholesterol

Urinalysis with microscopy

This shall be performed at Visit 1 and throughout the clinical study every time a subject makes a visit (shall be performed prior to administering the investigational product at Visits

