6.1.8 Visit 7 (Termination Visit, Day 270 ± 7) and Early Termination

Adverse event assessment

Confidential PRT NO: VMCMT-001 2021.06.07 98 / 99

Information on newly developed or worsened adverse events, or adverse events that disappeared since the last visit shall be collected.

Complete blood cell count

This shall be performed at Visit 1 and throughout the clinical study every time a subject makes a visit (shall be performed prior to administering the investigational product at Visits 2, 3, 4, and 5). However, if there is a subject with abnormal findings in the test at Visit 3 (Day 14), a complete blood cell count and a general blood chemistry test may be performed at Day 30 depending on the decision of the principal investigator.

The complete blood cell count items are as follows:

WBC, RBC, Hb, Hct, MCV, MCH, MCHC, PLT, ESR, MPV, differential count of WBC (Band neutrophil, Segmented neutrophil, Eosinophil, Basophil, Lymphocyte, Monocyte)

General blood chemistry test

This shall be performed at Visit 1 and throughout the clinical study every time a subject makes a visit (shall be performed prior to administering the investigational product at Visits 2, 3, 4, and 5). However, if there is a subject with abnormal findings in the test at Visit 3 (Day 14), a complete blood cell count and a general blood chemistry test may be performed at Day 30 depending on the decision of the principal investigator. Since a blood glucose test is included, the subject shall maintain an 8-hour fasting state prior to the test. The general blood chemistry test items are as follows:

total protein, albumin, globulin, A/G ratio, cholesterol, total bilirubin, AST, ALT, fasting glucose, BUN, creatinine, estimated GFR, Ca2+, phosphate, Na+, K+, Cl-, CRP, triglyceride, HDL-cholesterol, LDL-cholesterol

Sample collection for retrospective biomarker study

The serum of subjects shall be collected and stored frozen at -70°C. All blood samples are stored with unique numbers for retrospective biomarker study after all personal information is deleted.

Body measurement (weight measurement)

A subject's weight shall be measured at Visit 1 and throughout the clinical study every time a subject makes a visit (shall be performed prior to administering the investigational product at Visits 2, 3, 4, and 5).

Urinalysis with microscopy

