#### (5) HGF antibody production by Engensis (VM202)

The presence or absence of HGF antibody (anti-HGF Ab) in blood was verified with the ELISA method. A preliminary assessment was performed on whether antibody production is correlated between the subject group determined to have increased muscle mass and improved function, and the subject group not determined as such.

However, if antibodies in blood were not produced in any of the subjects, the results were not presented.

The antibody test for hepatocyte growth factor was performed at Visit 2 (Day 0) and Visit 7 (termination visit, Day 270) (performed prior to administration at Visit 2 [Day 0]).

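### With one post-dose anti-HGF sample, 166 days after the last dose, a negative means only that antibody was not detected at Day 270, not that none was generated

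*Protocol*

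**What the plan says.** Protocol 5.1 and SAP 1.1.2 list anti-HGF antibody generation by VM202 as the fifth secondary objective. Protocol 6.1.2.1 sets the sampling: "The antibody test for hepatocyte growth factor shall be performed at Visit 2 (Day 0) and Visit 7" (Day 270), with the Visit 2 sample taken before dosing. SAP 3.3 (5) repeats it: "The antibody test for hepatocyte growth factor was performed at Visit 2 (Day 0) and Visit 7 (termination visit, Day 270"). The schedule table in Protocol 6.1 marks the test at Visit 2, Visit 7 and early termination, and at no other visit.

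The last dose is at "Visit 5 (Fourth Administration, Day 104 ± 7"), and the post-dose sample falls at "Visit 7 (Termination Visit, Day 270 ± 7) and Early Termination".

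Protocol 8.4.4 (5) specifies a presence-or-absence ELISA, compares Day 270 with Day 0 by McNemar's test, and plans a preliminary look at whether antibody status goes with gains in muscle mass and function. SAP 4.8 (5) keeps the McNemar comparison. Protocol 8.4.4 (5), SAP 3.3 (5) and the synopsis all say that if no subject produced antibody, no results are presented.

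**The concern.** The objective covers the whole period after first dosing, but the measurement covers one day near the end of follow-up. A response after doses 1 and 2, or after doses 3 and 4, that has faded by Day 270 is classified as no antibody. The McNemar comparison and the look at antibody status against function both inherit that classification.

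The presentation rule adds to the problem. An all-negative Day 270 result is worded as antibodies not produced and then left out. A reader of the study report would see neither the denominator nor the single late time point behind the statement.

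**Working it through.** The documents state no dose-to-sample interval, so there is no figure of the plan's own to reproduce. The inputs are the visit days and windows in Protocol 6.1 and the sample size of 12 in Protocol 5.3.1.

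**Interval from dose to sample (completers)**
- Fourth dose to sample: 270 − 104 = 166 days.
- Shortest within windows: 263 − 111 = 152 days. Longest: 277 − 97 = 180 days.
- Second dose to sample: 270 − 14 = 256 days.

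A subject who leaves early is tested at the early termination visit. The interval can then be shorter, but there is still only one post-dose sample.

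**What an all-negative result supports**

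The exact (Clopper-Pearson) 95% upper limit for 0 of 12 is 1 − 0.025^(1/12) = 0.265, or 26.5%. This limit applies to being antibody-positive at Day 270.

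Extending it to ever having generated antibody needs a persistence figure that the documents do not give. Let s be the assumed share of subjects who ever made antibody and still test positive at Day 270, with no false positives. The upper limit becomes 26.5% / s, capped at 100%:

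| Assumed s | Upper limit for ever generating antibody |
|---|---|
| 1.0 | 26.5% |
| 0.8 | 33% |
| 0.5 | 53% |
| 0.3 | 88% |
| 0.25 or less | 100% (no information) |

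If half of subjects truly made antibody, the chance of seeing 0 of 12 positive is (1 − 0.5s)^12:
- s = 1: 0.0002
- s = 0.5: 0.03
- s = 0.2: 0.28

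These values show how far the conclusion depends on s. They do not estimate s.

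**What samples at existing visits would add**
- Day 90, pre-dose: 90 − 14 = 76 days after dose 2.
- Day 180: 180 − 104 = 76 days after dose 4 (173 − 111 = 62 to 187 − 97 = 90 within windows).
- Extra assays: 12 × 2 = 24 at most.

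**The case against.** The Day 0 and Day 270 pairing has a visible logic. Protocol 5.2 places the efficacy assessments at Visits 2 and 7, leg MRI is done only then, and the antibody result is to be related to muscle mass and function. The sample also follows all four doses. SAP 4.8 (5) already frames the comparison as Day 270 against Day 0. All of this stands. It supports having a Day 270 sample, but it does not make that sample a test of generation at any time.

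Prior concern is also low. Protocol 3.6 says the expressed HGF is identical to the native protein and acts locally, and Protocol 3.8 reports no anti-HGF antibody in the angina study. That makes a response less likely. It does not answer the question this study sets, at 56 mg in total against a tolerated dose of 2 mg in that study.

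A reader might infer three stronger things:
- **That the endpoint is worthless.** It is not. A positive is informative, and a negative argues against antibody persisting to Day 270.
- **That antibody must have gone by Day 270, because in the ALS study residual measurements** "showed that the drug was not detected at 3 months post-administration of VM202". That statement in Protocol 3.9 concerns residual product. Loss of the antigen source does not imply loss of antibody.
- **That an assumed half-life gives a fold-fall in titre and hence a miss rate.** The documents available give no peak time, half-life or assay sensitivity. Most of Protocol 3.8, including the ALS section, is not in the public text, so any rationale for the sampling time may sit there.

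The stored biomarker serum is not freely available for this test. At Day 90, "The serum of subjects shall be collected and stored frozen at -70°C", and likewise at Day 180. But Protocol 5.8 assigns it to a separate protocol, with separate human-materials consent and removal of personal information. Linkage may still exist, because Protocol 3.2 says the biomarker study will relate serum changes to symptom changes. The documents do not confirm it.

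**Conclusion.** The point holds in a limited form. For a completer, anti-HGF antibody is looked for once after dosing, 166 days (152 to 180) after the last dose. A negative establishes non-detection at Day 270 and cannot distinguish no response from a waned one. The wording of the objective and the non-presentation rule both claim more than that.

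The day arithmetic and the 26.5% limit rest only on the documents' visit days and on 12 tested subjects. Anything about the share of transient responses missed rests on assumed persistence, and the size of that loss is unknown. This is a worthwhile improvement to a secondary endpoint. It does not touch the primary safety endpoints as the plan defines them.

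**What to change.** 1. **Wording, in any case.** Define the existing endpoint as anti-HGF antibody present at Day 270 and limit the conclusion to that. Delete the rule that all-negative results are not presented. Report the count with its exact 95% interval; for 0 of 12 the upper limit is 26.5%. The cost is text only, and SAP 4.7 already uses the same interval method for adverse events.

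2. **Extra samples, where visits are still to come.** Take an anti-HGF aliquot from the blood already drawn at Day 90 (pre-dose) and Day 180, and include it in the planned single ELISA batch. Report any post-baseline positive alongside Day 270. This adds no visit and no extra venepuncture.

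3. **Where those visits have passed.** Protocol 5.7.1 says enrolment is complete, and the SAP describes the test in the past tense, so this may apply to many or all subjects. Use stored biomarker serum only if consent, subject linkage and remaining volume allow.

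Items 2 and 3 cost up to 24 extra ELISA samples and a protocol and consent amendment under Protocol section 16. The gain is partial, because each added sample is still about 76 days after the preceding dose, and a shorter-lived response could still be missed. If no extra samples can be tested, item 1 alone is enough to make the reported conclusion match the data.
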